**D.1.2. “Literacy and improving patient-clinician encounters for asthma,” (K02 HL088469; [name], PI),** is ongoing research examining whether limited health literacy, particularly numerical skills, hinders patient-physician communication and ultimately the ability to successfully self-manage asthma. We previously developed and validated the Asthma Numeracy Questionnaire (ANQ), a 4-item questionnaire derived from numerical concepts commonly used in patient instructions for self-managing asthma. ANQ scores indicated many adults do not understand the numerical concepts embedded in standard asthma education. Low ANQ scores were associated with hospitalizations and ED visits for asthma. We hypothesized that adequate literacy is associated with better health, mediated by patient-provider communication. We proposed a hierarchical model of numerical and communication skills to guide such communication.

The K02 Specific Aims test in participants of the parent WIN Study whether electronically-monitored inhaled steroid adherence, and asthma outcomes differ by literacy status. To the ongoing WIN Study, we added assessment of numeracy (ANQ) and reading comprehension, the Short Test of Functional Health Literacy in Adults (S-TOFHLA) to baseline questionnaires. In an analysis of the first 80 WIN participants for which we had literacy data, we found only 20% could answer all 4 ANQ items correctly. Less than half understood a question involving percentage (See Appendix, ANQ questionnaire, item 2). However, the reading comprehension score on the Short Test of Functional Health Literacy in Adults (S-TOFHLA) was adequate for 80% of participants. The ANQ results demonstrated that this test can distinguish among literacy levels. Additionally, higher ANQ scores were associated with better AQOL and self-efficacy to accomplish asthma self-management. The association of numeracy and AQOL supports a link between literacy and health.

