Preliminary analyses of the entire dataset for this analysis (n=284) adjusting for age, sex, race/ethnicity and the randomized intervention condition of WIN (PS vs AE), found that better adherence was associated with better numeracy ( $\beta = 2.70$ , 95% CI=[0.31, 5.10]) and reading comprehension ( $\beta = 10.17$ , 95% CI=[1.48, 18.9]). Similarly, higher AQOL was associated with better numeracy ( $\beta = 0.14$  [0.02, 0.26]) and reading comprehension ( $\beta = 0.63$  [0.18, 1.07]). Asthma control was associated with reading comprehension ( $\beta = 0.53$  [0.18, 0.88]). In summary, these findings support the need for an intervention directed at health literacy and communication as a pragmatic way of overcoming health disparities and improving asthma control.

**Conclusions:** Numerical concepts in patient education may be difficult for patients to understand. Low literacy, reading and numeracy, is associated with poorer health outcomes. A PAI that facilitates communication with health care personnel about health information may be able to improve asthma outcomes. These preliminary analyses support our proposed secondary aims assessing potential mediators such as self-efficacy and adherence, of the relationship between PA intervention and asthma control.

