**Table 2: Project Timeline**

Year	1	2	3	4	5										
Months	1-6	7-8	9-12	13-16	17-20	21-24	25-28	29-32	33-36	37-40	41-44	45-48	49-52	53-56	57-60
Start up: finalize IRB approval, finalize CRFs, train staff, create database															
New enrollment	50		100		100		50								
Follow-up															
Data analysis															
Focus groups: set up, conduct, analyze															
DSMB meets	x		x									x			

range of representative rates for those not employed. We will adjust costs for inflation using the Consumer and Medical Price Indices, as appropriate, and discount costs to the base year using a discount rate of 3%.

**D.9. Data Analysis:** We will perform descriptive analyses of all variables, then compare PA and UC groups for the adequacy of randomization, examining if covariates or baseline variables including potential moderators of the intervention and mediating relationships are equally distributed among patient groups. These baseline comparisons will be based on t-tests or Wilcoxon rank sum tests for continuous variables depending on the symmetry of the distributions, on logistic regression for binary or ordinal variables; and on Poisson log-linear regression for count data. If imbalances are found at baseline, the relevant variables will be treated as confounders in the ITT analyses and the analyses of mediators and moderators of the intervention on asthma control. To account for the potential for variation in the effectiveness of the intervention across physician practices, our analyses will compensate by including site as a fixed effect in all analyses. Analyses of PA and UC differences with respect to change from baseline at 6 and 12 months for each outcome in Aims 1 and 2 will be based on the ITT principle: all randomized subjects will be included in the analysis regardless of whether they drop out of the intervention or study. We will perform a sensitivity analysis of the missing at random assumption by following Bruce et al with a non-ignorable shared parameter model.

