The analysis will be based on random effects (RE) models applied to baseline and all follow-up visits at which outcome data are collected. The RE will be included to account for correlated and missing data. Separate time effects and time-treatment interactions will be specified for each follow-up visit, such that the treatment-time interaction for a particular visit will be the ITT effect on change since baseline. The RE models will be linear, logistic, and log-linear for continuous, binary, and count outcomes, respectively. Similar RE models will be employed for assessment of mediation and moderation in Secondary Aims 1 and 2.

**Data description, screening, and reorganization:** We will screen data for quality and integrity as proposed by Altman. For all variables we will determine measures of central tendency: mean and standard deviation for continuous variables, median and range for categorical variables. We will examine frequency distribution graphically (histograms, scatter plots) for all variables. Specific concerns will be directed to understanding the pattern of missing values, isolating outliers, confirming the homoscedasticity of observation groups, verifying the coding consistency, examining adherence to normality for variables anticipated to be so, and locating normalizing transformations for continuous variables intended to be investigated as such. For the tools we developed, we will examine internal consistency using Cronbach's  $\alpha$ .

**Addressing the impact of site on each outcome:** First, we will pool participants across sites, assuming no site effect, using logistic and regression modeling to isolate the relationship between outcome and exposure and other demographics. We have stratified randomization to analyze the effect of site. We have amplified the sample size (D.10) to have a large enough sample to conduct this analysis. As a secondary analysis, we will examine treatment-site interactions. In the presence of statistically significant interactions, we will present separate estimates of treatment effects for each site. In the case of statistically, but clinically marginally significant interactions, we will present main effect estimates of treatment effect but with interactions in the model using -1, 0, 1 dummy coding for site, so that the main effects' estimates will be for the average site.

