**Aims 1 & 2 (To assess whether PAI improves asthma control and other asthma outcomes):** The ITT effect of PA relative to UC on change in asthma control and other asthma outcomes since baseline at 6 months will be assessed with estimation and testing of the treatment-6 month visit interaction in the linear RE model (described above) with asthma control as the dependent variable. In addition, the treatment-12 month interaction will be tested and estimated to assess if the ITT effect is retained after the PA intervention ends.

**Secondary Aim 1 (Mediators):** The mediation analysis will follow the 4-step regression approach for testing mediated effects of Holmbeck. First, we will examine the association between PAI and mediators (D.8.2) by fitting separate longitudinal RE models with each mediator as the dependent variable. These models will test the effects of the PAI relative to the UC group with respect to change since baseline at each follow-up visit for the potential mediators. Second we examine the association between the PAI and asthma control as described in Aim 1. Third, we will assess the relationship between the mediators and asthma control by fitting separate longitudinal RE models with the mediators (D.8.2) as the independent variables and asthma control as the dependent variable. Finally, the mediators with significant effects at steps 1 and 3 will be included as a lagged time-varying covariate in the ITT linear RE model for asthma control in Aim 1. Mediators of the PAI will be assessed by comparing the randomization (intervention) effect estimate with and without the potential mediator in the model. A reduction of at least 15% in the treatment-visit interaction parameters at 6 and 12 months due to the inclusion of the mediator in the model will be the criteria for a significant mediator.

**Secondary Aim 2: Moderators** of the intervention (D.8.3) will be tested and estimated with 3- and 2-way interactions among the treatment factor, potential moderator, and visit factor in the ITT model in Aim 1. Similarly, moderators of the mediating relationship will be assessed with 3- and 2-way interactions among the treatment factor, mediator, potential moderator, and visit factor in the mediation model in Secondary Aim 1.

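### Apart from site, baseline covariates enter the mediation models only if the arms are imbalanced, which is the wrong trigger for confounding of the mediator-outcome path

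*Combined protocol and SAP*

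**What the plan says.** D.9 (Data Analysis) first compares the arms, "examining if covariates or baseline variables including potential moderators of the intervention and mediating relationships are equally distributed among patient groups". It then gives the rule: where imbalance is found, "the relevant variables will be treated as confounders in the ITT analyses and the analyses of mediators and moderators". Site is handled separately, by "including site as a fixed effect in all analyses". No threshold for imbalance is given.

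The outcome analysis uses "random effects (RE) models applied to baseline and all follow-up visits at which outcome data are collected", with a treatment-by-visit term for each follow-up visit, and D.9 says that models of a similar kind serve mediation and moderation. Under Secondary Aim 1, step 3 reads: "we will assess the relationship between the mediators and asthma control by fitting separate longitudinal RE models with the mediators" as the independent variables. Step 4 adds mediators that are significant at steps 1 and 3, lagged, to the Aim 1 model. A mediator is declared if the treatment-by-visit terms at 6 and 12 months shrink by at least 15%. There is no interval or test for the indirect effect.

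Numeracy, reading comprehension, education, income, depressive symptoms, trait anxiety and smoking are baseline measures (D.8.3). They are used as moderators, so they meet the mediators only in the Secondary Aim 2 interaction models.

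**The concern.** Balance between arms bears on the comparison of the arms. It says nothing about why one patient has higher self-efficacy or better adherence than another. A stable trait that raises the mediator and improves asthma control produces a mediator-control slope with no causal content. Randomisation balances that trait across arms but leaves its links to mediator and outcome intact. A rule triggered by imbalance therefore passes over the variables that matter here.

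The protocol's own data (D.1.2) make such traits plausible. Reading comprehension was related to electronically monitored adherence, and "Asthma control was associated with reading comprehension". Also, "higher ANQ scores were associated with better AQOL and self-efficacy to accomplish asthma self-management". D.8.2 describes one self-efficacy item, confidence with medical forms, as correlating with a standard literacy test.

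At stake is Secondary Aim 1. A confounded slope helps a variable pass step 3, and step 4 then removes (intervention effect on mediator) x (confounded slope) from the treatment effect, which the plan reads as mediation.

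**Working it through.** **1. The plan's effect size.** Inputs from D.10: 150 per arm, 18% dropout (123 per arm), two-sided alpha 0.025, 80% power, intraclass correlation 0.30, 3 measures at 6 months.

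(2.241 + 0.842) x sqrt(2/123) x sqrt((1 + 0.30 x 2)/3) = 0.393 x 0.730 = 0.287, against the stated 0.29. I use 0.29 SD as the total effect.

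**2. What the 15% criterion needs.** 0.15 x 0.29 = 0.0435 SD. If the intervention moves the mediator by 0.5 SD (assumed), a spurious slope of 0.0435/0.5 = 0.087 is enough. At 0.3 SD it is 0.145 and at 0.8 SD it is 0.054.

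**3. How often a balanced confounder enters.** At an assumed p<0.05, about 5% per variable; for at least one of 10 independent variables, 1 - 0.95^10 = 40%.

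**4. Confounder strength in the documents.** From the D.1.2 intervals (n=284, about 278 df), SE = interval width/3.92, t = beta/SE, r = t/sqrt(t² + df):

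| Pair | beta [95% CI] | t | r |
|---|---|---|---|
| Reading comprehension, adherence | 10.17 [1.48, 18.9] | 2.29 | 0.14 |
| Numeracy, adherence | 2.70 [0.31, 5.10] | 2.21 | 0.13 |
| Reading comprehension, asthma control | 0.53 [0.18, 0.88] | 2.97 | 0.18 |

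The largest literacy-mediator correlation in the documents is 0.35 (Navigating Ability with numeracy, D.8.2).

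**5. Spurious fall under the plan's model.** Take a mediator with zero effect on control and one stable confounder with correlation r_M to the mediator and r_Y to control, better literacy going with better values of both. Use a random-intercept model with T = 5 rows including baseline, outcome correlation rho = 0.30 and mediator intraclass correlation k (assumed 0.3 to 0.6). The fitted slope has magnitude

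b = [T r_M r_Y/(1+(T-1)rho)] / [(T-1)(1-k)/(1-rho) + (1+(T-1)k)/(1+(T-1)rho)].

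The fall is 0.5 x b/0.29. For k = 0.5 and r = 0.4 on both paths: numerator 5 x 0.16/2.2 = 0.364; denominator 4 x 0.5/0.7 + 3/2.2 = 4.221; b = 0.086; fall = 14.9%.

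| r_M / r_Y | Formula, k = 0.3 to 0.6 | Simulated | Confounder adjusted |
|---|---|---|---|
| 0.14 / 0.18 (D.1.2) | 2.0-2.6% | about 2% | about 0% |
| 0.35 / 0.18 | 4.9-6.4% | 5-7% | about 0% |
| 0.3 / 0.3 (assumed) | 7.1-9.2% | 8-9% | about 0% |
| 0.4 / 0.4 (assumed) | 12.5-16.4% | 13-16% | about 0% |

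**6. Passing the whole rule.** I simulated 246 completers (450 runs per scenario, standard error at most 2.3 points), requiring p<0.05 at steps 1 and 3 and a 15% fall at both 6 and 12 months. The mediator has zero effect and k = 0.50. Each range runs from a confounder acting only after baseline to one with constant effect.

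| Loading on both paths (assumed) | No adjustment | Plan's rule | Always adjusted |
|---|---|---|---|
| 0 | 0.9% | 0.9% | 1.1% |
| 0.3 | 6.7-10.2% | 6.0-10.2% | 0.7-0.9% |
| 0.4 | 18.2-35.6% | 17.3-34.7% | 1.1% |
| 0.5 | 34.4-67.8% | 32.4-64.4% | 0.2% |

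The plan's rule performs almost like no adjustment. If a significant 6-month treatment effect (step 2) is also required, its rates fall to 0.7-1.8%, 1.6-7.6% and 8.2-24.0% at loadings 0.3, 0.4 and 0.5, against 0-0.2% with adjustment.

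**The case against.** The strongest reply is about size. At the strength seen in D.1.2 the spurious fall is about 2%, and even 0.35 with 0.18 gives 5-7%. The evidence is also indirect. Adherence in D.1.2 was monitored electronically, while the trial's mediator is self-report, which correlated only 0.23 with monitored adherence (D.8.2). The 0.35 comes from 31 patients with p=0.057. All of this stands. A reader might infer that documented literacy confounding alone can make an inert variable pass as a mediator; the documents do not support that.

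Three other inferences also go too far.

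- That confounders are always shut out: site always enters, and a balanced variable can be flagged by chance.
- That step 3 omits treatment: the step 3 sentence does not name it, but D.9's statement that the mediation models resemble the outcome models plausibly puts it there. This is a point to state, not an established omission.
- That a wrong mediator would decide which advocate activities are kept: no section ties the mediation results to such a decision.

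The random intercept and the lag do not answer the point. The intercept absorbs part of a stable confounder, and both features are in the simulation of step 6. What the reply leaves untouched is that arm imbalance does not identify mediator-outcome confounders.

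**Conclusion.** The concern holds as one about the adjustment rule. Apart from site, D.9 selects covariates for the mediation models by a criterion that does not address confounding of the mediator-control path, and in simulation it protects hardly better than no adjustment. The bias for one confounder runs from about 2% of the treatment effect at documented strength to 13-16% at an assumed 0.4 on both paths. Only the top of that range reaches the 15% criterion. Several confounders acting together could also reach it; the documents measure many candidates but do not give their joint strength.

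The figures assume a 0.5 SD intervention effect on the mediator, a 0.29 SD total effect, an outcome correlation of 0.30 and a zero-effect mediator. Only the 0.29 and 0.30 come from the plan. The point is confined to the mediation analysis and its interpretation; Aims 1-3 do not depend on it.

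**What to change.** In steps 3 and 4 always include, whether or not balanced between arms:

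- treatment and treatment-by-visit terms, and site;
- numeracy (ANQ), reading comprehension (S-TOFHLA), education, household income, depressive symptoms (CES-D), trait anxiety and smoking;
- age, sex and race/ethnicity, as in the team's own analysis in D.1.2.

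Keep baseline asthma control as a response row, as D.9 has it, and do not also enter it as a covariate. If the mediation models are instead fitted to follow-up visits only, adjust for baseline asthma control and the baseline mediator.

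State that the result assumes no unmeasured or post-baseline mediator-outcome confounding. Baseline covariates cannot remove the latter, so add a simple sensitivity analysis, for example how strong a remaining confounder would have to be to bring the fall below 15%.

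The cost is a change to the analysis text, a few degrees of freedom and a little more analysis. The variables are already planned measures, so no new data collection is needed.

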**Specific Aim 1:** The power analysis is based on the 2-sample t-test with adjustments for 3 or 5 repeated measures per participant. The adjustment for clustering by patient multiplies the estimated sample size under simple random sampling by a design effect,  $d=1+\rho(n-1)$ , where  $n$ =average number of visits per patient, and  $\rho$  is the patient intraclass correlation. We apply a conservative intraclass correlation of 0.30. The power analysis also takes into consideration the following factors: 1) 18% drop-out as observed in WIN; 2) adjusted 2-sided significance level of 0.025; and 3) 80% power. With these factors, the study is powered to observe a standardized effect of 0.29 and 0.32 difference in mean change in asthma control across intervention groups at 6 months and 12 months, respectively. **Specific Aim 2:** The power analysis examines the intervention effect on 5 asthma outcome measures at 6 and 12 months. Using the same assumptions but with 2-sided  $\alpha=0.005$  to conservatively adjust for multiple comparisons, we will have 80% power to detect a standardized effect of 0.34 and 0.31 between groups at 6 months and 12 months, respectively. **Specific Aim 3:** Power for the economic analysis (costs have greater variability than clinical outcomes) is 81% based on the same effect size, 2-sided  $\alpha$  of 0.05, an effect-cost correlation of -0.1, a difference in cost of \$500 and a willingness to pay (WTP) threshold of \$2500 per year of improved adherence or avoided hospitalization. An increase in the WTP to \$3000 results in 98% power. Thus, the sample size will provide sufficient statistical power for assessment of both clinical and economic evaluations (which requires detecting both effect and cost differences).

**D.11. Data Management:** The Clinical Research Computing Unit will collaborate to finalize CRFs, construct the database, protect its security, perform data entry, review, query and update data; assist with preparation of DSMB reports, and collaborate with biostatisticians as it has for HAP and WIN studies.

**D.12. The Data Safety Monitoring Board** (see Human Subjects) will meet at study start, year 2, and year 5. At these and every 6 months the DSMB will review reports of accrual, baseline comparability between PA and UC groups, adverse events, safety concerns, data quality, maintenance of confidentiality and recommend study modifications and whether the study can continue.

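### The primary model leaves its random effects unspecified; with a random intercept only and correlation that falls over time, the 12-month test would exceed its 0.025 level

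*Combined protocol and SAP*

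**What the plan says.** D.9 Data Analysis sets out one longitudinal model for Aims 1 and 2: "The analysis will be based on random effects (RE) models applied to baseline and all follow-up visits at which outcome data are collected". The mean structure is clear: each follow-up visit has its own time effect and its own interaction with treatment. The coding is chosen "such that the treatment-time interaction for a particular visit will be the ITT effect on change since baseline".

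The correlation structure gets one sentence: "The RE will be included to account for correlated and missing data". D.9 does not say whether the random effects are intercepts, slopes or both. It gives no residual covariance and no robust standard error. The one sensitivity analysis it names for this model concerns the missing-at-random assumption.

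D.10 Sample size makes asthma control at Visit 3 (6 months) and Visit 5 (12 months) the primary outcome. D.9 says of the second time point that "the treatment-12 month interaction will be tested and estimated to assess if the ITT effect is retained after the PA intervention ends". The Aim 1 power calculation uses an "adjusted 2-sided significance level of 0.025". It is also the only place where within-patient correlation gets a number: "We apply a conservative intraclass correlation of 0.30". That number enters a design effect: "The power analysis is based on the 2-sample t-test with adjustments for 3 or 5 repeated measures per participant".

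**The concern.** The 12-month contrast compares the two visits furthest apart, baseline and week 48. A random intercept treats every pair of visits as equally correlated, so each contrast gets a standard error based on the average correlation. If correlation falls with time, baseline and week 48 are the least correlated pair, and the model understates the variance of their difference.

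Falling correlation is plausible here. The asthma control score covers the past week (D.8.1), visits span 48 weeks (Table 1), D.5 acknowledges seasonal variation, and the intervention ends at 6 months (D.2.2). At stake is the sustainability half of Aim 1. A false finding that the effect persists would be more likely than 0.025 allows. Because the random effects are not named, the choice could also be made after the data are seen.

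**Working it through.** **The plan's own figures.** The documents give a nominal level of 0.025 but no achieved type I error, so there is nothing to reproduce on that quantity. To see how the intraclass correlation is used, I reproduced the Aim 1 detectable effects.

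- Evaluable per arm: 150 × 0.82 = 123.
- Effective n = 123k / (1 + 0.30(k − 1)).
- Detectable effect = (2.241 + 0.842) × √(2 / effective n).
- k = 3: effective n 230.6, effect 0.287 (stated: 0.29).
- k = 5: effective n 279.5, effect 0.261 (stated: 0.32).

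The 12-month figure does not follow from the stated inputs and needs separate attention; nothing below depends on it. The 0.30 is therefore an input to a t-test power formula.

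**Type I error with a random intercept only.** Assume complete data at the five visits and equal variance at each. The visit means are saturated, so the estimated treatment effect is the same under any of these covariance models; only its standard error changes. The fitted common correlation is r̄, the mean over the 10 visit pairs (4, 3, 2 and 1 pairs at lags of 12, 24, 36 and 48 weeks).

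- q = model SE / true SE = √((1 − r̄) / (1 − r48)) at 12 months, with r24 in place of r48 at 6 months.
- Type I error = 2 × (1 − Φ(2.241 × q)).

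Mild decay, 0.35/0.30/0.25/0.20: r̄ = (4×0.35 + 3×0.30 + 2×0.25 + 0.20)/10 = 0.30. q = √(0.70/0.80) = 0.935. Type I error = 0.036.

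AR(1) with lag-1 correlation 0.494: r̄ = 0.301 and r48 = 0.060. q = √(0.699/0.940) = 0.862. Type I error = 0.053.

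**Type I error with a random intercept and slope.** No closed form was used. The intercept-slope covariance plus independent residual was fitted to each assumed correlation matrix by minimising log|V| + tr(V⁻¹R). The model and true variances of each change were then compared in the same way.

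All correlation patterns below are assumptions.

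| Correlation at 12/24/36/48 weeks | r̄ | q, 12 mo, intercept only | Intercept only, 12 mo | Intercept only, 6 mo | With slope, 12 mo | With slope, 6 mo |
|---|---|---|---|---|---|---|
| Constant 0.30 | 0.300 | 1.000 | 0.0250 | 0.0250 | 0.0250 | 0.0250 |
| 0.2 + 0.2×0.6^lag | 0.281 | 0.964 | 0.0307 | 0.0259 | 0.0229 | 0.0266 |
| 0.35/0.30/0.25/0.20 | 0.300 | 0.935 | 0.0360 | 0.0250 | 0.0235 | 0.0261 |
| 0.60/0.55/0.50/0.45 | 0.550 | 0.905 | 0.0426 | 0.0250 | 0.0228 | 0.0268 |
| 0.50/0.40/0.30/0.25 | 0.405 | 0.891 | 0.0459 | 0.0256 | 0.0203 | 0.0281 |
| AR(1), 0.494 | 0.301 | 0.862 | 0.0533 | 0.0311 | 0.0169 | 0.0355 |
| 0.70/0.60/0.50/0.40 | 0.600 | 0.816 | 0.0672 | 0.0250 | 0.0212 | 0.0292 |
| AR(1), 0.7 | 0.520 | 0.795 | 0.0747 | 0.0296 | 0.0172 | 0.0361 |
| AR(1), 0.9 | 0.814 | 0.735 | 0.0996 | 0.0267 | 0.0186 | 0.0351 |

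**Simulation with dropout.** Null trials of 300 patients with 18% monotone dropout and a random-intercept REML fit gave 12-month rejection rates of 0.026 (constant 0.30; 4,000 trials), 0.050 (AR(1) 0.494; 2,500) and 0.074 (AR(1) 0.7; 2,500). These agree with the table. With a slope added, 400 trials each for AR(1) 0.494 and 0.7 gave 0.015 and 0.005 at 12 months and 0.0225 and 0.0375 at 6 months. That is too few trials for precise rates, but it confirms no 12-month inflation.

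**The case against.** The strongest reply is that the plan never commits to a random intercept. D.9 says random effects and no more, and a simplification in a power formula does not fix the covariance of the analysis model. A model with a random slope fits the wording equally well, and it shows no 12-month inflation under any pattern tried. The documents also give no correlations by lag, so the amount of decay is a judgement.

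All of this stands, and it rules out two stronger readings. A reader might infer that the primary model has one intraclass correlation for all visit pairs; the documents attach that figure only to the sample size. A reader might also infer that the 12-month error rate doubles. It roughly does under AR(1) averaging 0.30, but it is about 1.2 to 1.4 times nominal under the two mildest patterns and 4 times under the strongest.

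Nor do the calculations show that dropout makes matters worse. For the three stepped patterns starting at 0.60, 0.50 and 0.70, simulated rates with 18% dropout were 0.049, 0.050 and 0.058, against 0.043, 0.046 and 0.067 analytically.

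The slope does not settle the matter, though. Under decay it makes the 12-month test conservative and moves some of the error to the 6-month test. Neither choice holds both tests at 0.025 under the decay patterns examined, and the plan names neither.

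**Conclusion.** The point holds as a conditional one and should be fixed. The model behind both primary tests relies on unspecified random effects for within-patient correlation, with nothing to protect the standard error if they are wrong.

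With an intercept only and correlation falling over time, 12-month type I error is about 0.03 to 0.075 instead of 0.025, reaching about 0.10 under very strong AR(1). With a slope added, it is about 0.017 to 0.024 at 12 months and about 0.026 to 0.036 at 6 months. With constant correlation, both tests hold their level.

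These figures assume equal variances across visits and, for the table, complete data and large-sample normal tests. They concern the linear model only; the logistic and log-linear models were not examined.

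**What to change.** For the continuous outcomes in Aims 1 and 2 (asthma control, quality of life, FEV1), keep the planned visit and treatment-by-visit means. Specify an unstructured within-patient covariance across the five visits, fitted by REML with Kenward-Roger degrees of freedom. Name the fallback in advance if it does not converge, for example heterogeneous AR(1), or stated random effects with robust standard errors. Settle this before outcome data are examined by arm.

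Use the same covariance in the linear mediation and moderation models that reuse the Aim 1 model. In particular, the two fits compared under the 15% mediation criterion should share it. The shared-parameter sensitivity analysis can keep its own random effects, but the text should state how it relates to the revised primary model.

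The cost is a short wording change in D.9, with those sections aligned, and up to 15 covariance parameters (5 variances and 10 covariances), which 300 participants support easily. If correlation is in fact constant, the loss of efficiency is negligible.

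### D.9 does not say whether the two arms share one baseline mean in the primary model; if they do not, the treatment contrast is unbiased but less precise than the data allow

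*Combined protocol and SAP*

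**What the plan says.** Section D.9 (Data Analysis) bases Aims 1 and 2 on "random effects (RE) models applied to baseline and all follow-up visits at which outcome data are collected", so baseline is a response and not only a covariate. On the fixed terms it says: "Separate time effects and time-treatment interactions will be specified for each follow-up visit". It then gives the meaning attached to each of these interaction terms, namely that they are set up "such that the treatment-time interaction for a particular visit will be the ITT effect on change since baseline". The comparison is described elsewhere in D.9 as "PA and UC differences with respect to change from baseline at 6 and 12 months for each outcome". Under Aims 1 and 2, the 6-month and 12-month interactions are the ones estimated and tested.

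On baseline adjustment, D.9 says: "If imbalances are found at baseline, the relevant variables will be treated as confounders in the ITT analyses". Nothing in D.9 adjusts for baseline asthma control unconditionally, says that the arms have one baseline mean, or says that they have separate ones.

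Section D.10 supplies the correlation: "We apply a conservative intraclass correlation of 0.30". It is introduced for a design effect, not as a baseline-to-follow-up correlation.

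**The concern.** In a randomised trial the arms have equal baseline means in expectation. A model with a free treatment term at baseline spends information on estimating a difference known to be zero, and its treatment-by-visit interaction subtracts the whole observed baseline difference. When baseline predicts follow-up only weakly, that subtraction adds more noise than it removes. A model with one common baseline mean, or with baseline as a covariate, subtracts only the predictive part.

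The wording in D.9 allows either model, so two competent analysts could fit different primary analyses from it, and the choice could be made after the data are seen. At stake is the precision of the Aim 1 and Aim 2 tests, in a trial where D.10 expects a group difference smaller than the individual-level 0.5 and cites two earlier differences, 0.2 and 0.32, neither statistically significant.

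**Working it through.** **Inputs.** From D.10: 150 per arm; 18% dropout, so 150 × 0.82 = 123 completers per arm; two-sided alpha 0.025 for Aim 1; 80% power; intraclass correlation 0.30; "adjustments for 3 or 5 repeated measures per participant". Normal quantiles: 2.241 + 0.842 = 3.083.

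**The plan's own figure.** The design effect is 1 + 0.30 × 2 = 1.6 for three measures. The effective number per arm is 123 × 3/1.6 = 230.6, and 3.083 × √(2/230.6) = 0.287. The stated 0.29 at 6 months is reproduced. (With five measures the same formula gives 0.261, not the stated 0.32. That is a separate matter, and the 0.32 is not needed for the variance ratio below.) The reproduced formula describes an average over visits, not a change contrast at one visit, so it does not show which baseline structure was intended.

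**Variance of the two contrasts.** Take the linear model, complete data, equal variance σ² at each visit and correlation rho between baseline and the visit tested. The variance of the treatment contrast is 2vσ²/n, with
- treatment term at baseline (raw difference in change): v = 2(1 − rho)
- common baseline mean, or baseline as covariate: v = 1 − rho²
- ratio: 2(1 − rho)/(1 − rho²) = 2/(1 + rho)

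| rho | change | shared baseline | ratio |
|---|---|---|---|
| 0.30 | 1.40 | 0.91 | 1.54 |
| 0.50 | 1.00 | 0.75 | 1.33 |
| 0.70 | 0.60 | 0.51 | 1.18 |
| 0.80 | 0.40 | 0.36 | 1.11 |

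Inverting the generalised least squares information matrix of a five-visit random-intercept model, with and without the treatment main effect, gives the same ratios at 0.30, 0.50 and 0.70.

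**Dropout.** D.10 gives only the total of 18%. Assume a monotone pattern per arm of 123 with all five visits, 7 each stopping after four, three and two visits, and 6 with baseline only, all kept in the model. At rho 0.30 the variances are 0.0198 versus 0.0133 at 6 months (ratio 1.49) and 0.0211 versus 0.0146 at 12 months (ratio 1.45).

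**Detectable effect.** With 123 completers per arm, rho 0.30 and effects in single-visit SD units:
- change: 3.083 × √(2 × 1.40/123) = 0.465 SD
- shared baseline: 3.083 × √(2 × 0.91/123) = 0.375 SD

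To match the shared-baseline precision, the change contrast would need 123 × 1.54 ≈ 189 completers per arm.

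**Power depends on the scale of the effect.** At 0.32 single-visit SD, power is 45% versus 65%. If 0.32 is in units of the SD of change, it equals 0.32 × √1.40 = 0.379 visit SD, and power is 61% versus 81%. D.10 does not say which SD standardises the effect. The variance ratio is the same either way.

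**The case against.** The strongest objection is that the listed terms already describe a shared-baseline model: time effects and treatment interactions at the follow-up visits, with baseline as a response and no treatment main effect named. Read literally, the penalty is zero. The change-from-baseline wording does not contradict this, because a common-baseline model estimates the same quantity.

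This stands as a possible reading, but it is not established. The list is not exhaustive: it omits the intercept, and also site, which D.9 includes elsewhere as a fixed effect. The two- and three-way interactions among treatment, moderator and visit in Secondary Aim 2 fit the conventional model with a treatment term at baseline. Testing baseline differences and then adjusting for those found also sits oddly with means held equal by design.

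Conversely, a reader might infer that the plan fits separate baseline means and so loses 54% in variance. The documents do not support that either. No sentence puts a treatment main effect in the model, and the 0.30 equals the baseline-to-visit correlation only under compound symmetry, as a random intercept implies.

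Nor can the figure be carried to ED visits, hospitalisations or other event outcomes. The formula is for the linear model, and the documents give no visit-to-visit correlation for counts.

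Finally, the difference in change is a valid intention-to-treat estimator. The point concerns precision and specification, not bias.

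**Conclusion.** The point holds as an ambiguity with a conditional cost. D.9 leaves open whether a treatment term is fitted at baseline, and its only baseline adjustment depends on observed imbalance. For asthma control and other continuous outcomes, the excess variance is zero if that term is absent. If it is present, the excess with complete data is 54% at rho 0.30, falling to 33% at 0.5 and 18% at 0.7; at rho 0.30 it is 49% at 6 months and 45% at 12 months under the assumed dropout pattern. These figures rest on equal variances across visits and, at 0.30, on reading the design-effect correlation as the baseline-to-visit correlation. No size is claimed for binary or count outcomes. Because the choice affects the primary test and costs nothing to settle, it should be settled before analysis.

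**What to change.** Add to D.9 that the linear random effects model for asthma control and the other continuous outcomes keeps baseline as a response row, with one common baseline mean and no treatment term at baseline. The alternative is to model follow-up values only, always with baseline value by visit as a covariate. Either should apply regardless of observed imbalance, so that the rule on imbalanced variables does not decide whether the baseline outcome is adjusted for.

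For binary and count outcomes, specify the common-baseline form. Do not describe it as equivalent to covariate adjustment: in a logistic model, conditioning on baseline changes the odds ratio being estimated. Do not claim the same numerical gain.

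The cost is a sentence or two of text, with no new data or participants. In the linear model the estimand is unchanged, because randomisation makes the baseline means equal in expectation. If a common baseline was already intended, the addition only records it.
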